#### 14.0 REGISTRATION GUIDELINE

14.1 Forms and records needed for registration will include: Informed Consent, Patient's Bill of Rights, and HIPAA form.

14.2 At the time of registration, three copies of a signed and dated patient Informed Consent form with Bill of Rights will be available (an original for patient's medical chart; one copy for the patient; and the other for the PI's file).

## 15.0 BIOHAZARD CONTAINMENT

N/A

## 16.0 ETHICAL AND REGULATORY CONSIDERATIONS

All institutional and Federal regulations concerning the Informed Consent form will be fulfilled. The study will be conducted in adherence to ICH Good Clinical Practice.

## Appendix III – Data collection sheet

### Prunes study screening questionnaire

#### Screening questions

Are any of the following exclusion criteria met?                      Yes                      No

1. Under age 18
2. Diabetes mellitus
3. Inflammatory bowel disease, gastroparesis, or other bowel disorder
4. History of bowel resection or presence of colostomy
5. Regular (at least weekly) laxative use
6. At least one bowel movement each week
7. Allergy to docusate or prunes
8. Unable or unwilling to take docusate or prunes for any reason
9. Unable to give informed consent
10. Unwilling to follow protocol
11. Emergency surgery
12. Outpatient surgery
13. Active malignancy

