### 5.2 Exclusion Criteria

1. Unable to give informed consent
2. Unwilling to follow protocol
3. Active malignancy

4. Emergency surgery
5. Diabetes mellitus
6. Inflammatory bowel disease, gastroparesis, or other bowel disorder
7. History of bowel resection or presence of colostomy
8. Dependence on regular laxative use prior to surgery
9. Baseline frequency of bowel movements less than weekly
10. Intraoperative enterotomy or any bowel surgery performed at the time of surgery
11. Patient unable to initiate oral intake on post op day 1 for any reason
12. Allergy to docusate or prunes

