## 6.0 STRATIFICATION/DESCRIPTIVE FACTORS/RANDOMIZATION SCHEME

6.1 Stratification factors. N/A

6.2 Descriptive factors. Age, height, weight, self-described race and ethnicity, menopausal status, baseline frequency of bowel movements, laxative use, fiber use, medications used, and baseline stool consistency.

6.3 Randomization plan:

On morning of post-operative day 1, participants who do not meet exclusion criteria will be randomized to the treatment or control group at a 1:1 ratio. Randomization blocks of 6 will be applied in this study to ensure balanced treatment assignments throughout the recruitment period. The randomization assignment list will be generated by the study statisticians. [name]. Ph.D

Participants will be standardly administered 100 g of docusate twice daily for three days per existing routine post-operative care. In addition, we will administer a total of 12 oz of prunes to the study group which are pitted and preservative free. The prunes will be provided to the participant in a sealed package. The study group be instructed to eat 4 oz of prunes daily. The control group will be advised to avoid prune products for 3 days. Each group will be given a diary to note their prune and/or docusate consumption and details of their first bowel movement.

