**If Yes to any of the above, do not enroll.**

# Prunes Data Collection Sheet

## Baseline data collected at time of study enrollment

Participant number # \_\_\_\_\_

Age \_\_\_\_\_ years

Race            White    Black or African American    Asian  
                  American Indian or Alaska Native    Native Hawaiian or Pacific Islander  
                  Other    Multiple races

Hispanic Ethnicity            Yes            No

Parity \_\_\_\_\_

Height            \_\_\_\_\_ cm

Weight            \_\_\_\_\_ kg

Menopausal            Yes            No            Unsure/Not known

Baseline frequency of bowel movements

Multiple times daily            Once a day            Once every other day  
 Twice a week            Once a week

Have you needed to use a laxative at any time in the last 3 months?            Yes            No

Do you take fiber daily or almost daily?            Yes            No

Are you on any of the following medications on a regular basis?            Yes            No

Antimuscarinics (such as Detrol, Ditropan)            Yes            No            No

Iron            Yes            No            No

Calcium channel blocker (such as nifedipine, amlodipine, verapamil, diltiazem)            Yes            No            No

Opioids (such as Percocet, Oxycodone, Tramadol, etc.)            Yes            No            No

Tricyclic antidepressant (such as amitriptyline, imipramine)            Yes            No            No

Bristol Stool Scale (Describe usual stool consistency) \_\_\_\_\_ (Indicate number)

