# Prunes Data Collection Sheet

## Data collected at time of randomization

Are any of the following exclusion criteria met?                      Yes                      No

1. Intraoperative enterotomy or any bowel surgery (not including posterior colporrhaphy) performed at the time of surgery
2. Patient unable to initiate oral intake on post op day 1 for any reason

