### If Yes to any of the above, do not randomize.

Was preoperative bowel prep administered?                      Yes                      No

Primary indication for surgery

- Adnexal mass
- Abnormal uterine bleeding (with or without fibroids)
- Fibroid uterus (without abnormal uterine bleeding)
- Pelvic organ prolapse
- Other (Please indicate) \_\_\_\_\_

Procedures performed

- Open abdominal hysterectomy
- Open sacral colpopexy
- Open surgery, other
- Vaginal hysterectomy
- Other vaginal only surgery
- Laparoscopic or robotic hysterectomy (including laparoscopic or robotic assisted vaginal hysterectomy)
- Laparoscopic or robotic sacral colpopexy
- Laparoscopic or robotic surgery, other
- Posterior colporrhaphy
- Burch urethropexy alone
- Other (Please indicate) \_\_\_\_\_

Estimated blood loss \_\_\_\_\_ ml

Surgery start time \_\_\_\_\_

Surgery end time \_\_\_\_\_

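### Screening form item 6 reverses protocol exclusion 9, so as printed no woman is eligible under both

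*Combined protocol and SAP*

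**What the plan says.** Section 5.2 of the protocol lists twelve exclusion criteria. Item 9 is "Baseline frequency of bowel movements less than weekly".

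The screening questionnaire in Appendix III applies the exclusions that can be judged before surgery. Its 13 items stand under the question "Are any of the following exclusion criteria met". Item 6 is "At least one bowel movement each week". The list closes with "If Yes to any of the above, do not enroll".

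The baseline data sheet in the same appendix records usual bowel frequency in five categories. The highest is "Multiple times daily" and the lowest is once a week. No category lies below weekly.

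A second eligibility check is made at randomization. It has two items: "Intraoperative enterotomy or any bowel surgery (not including posterior colporrhaphy) performed at the time of surgery", and inability to start oral intake on the first postoperative day. It ends "If Yes to any of the above, do not randomize". Section 6.3 says that "participants who do not meet exclusion criteria will be randomized to the treatment or control group at a 1:1 ratio".

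**The concern.** Item 6 describes the state the protocol requires, yet it sits in a list where a positive answer bars enrolment. It is the only item on either form that tests exclusion 9.

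There are two ways to use the form, and neither is satisfactory:

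- **Followed literally**, it rejects the whole intended population on this criterion and passes only women with infrequent bowel movements, whom the protocol excludes. The primary endpoint is time to first bowel movement, so this is a criterion closely tied to the outcome.
- **Read by intent**, staff must disregard a printed instruction not to enrol. The screening sheet then cannot show that exclusion 9 was applied, because its printed content contradicts the decision taken.

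What is at stake is who is enrolled and whether eligibility can be verified from the screening record.

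**Working it through.** The plan gives no figure of its own on this point, so the check is one of logic.

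**Inputs.** Let *f* be baseline bowel movements per week.

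- Section 5.2, item 9: exclude if *f* < 1. Eligible on this criterion if *f* ≥ 1.
- Appendix III, screening item 6 with its closing instruction: do not enrol if *f* ≥ 1. Eligible if *f* < 1.
- Appendix III, baseline sheet: five frequency categories, all with *f* ≥ 1. A sixth state, below weekly, is added here to complete the range.

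**Both rules applied to each state.**

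| Baseline frequency | Eligible under section 5.2 | Eligible under item 6 as printed | Eligible under both |
|---|---|---|---|
| More than once a day | yes | no | no |
| Daily | yes | no | no |
| Every second day | yes | no | no |
| Two per week | yes | no | no |
| One per week | yes | no | no |
| Below weekly | no | yes | no |

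Section 5.2 passes 5 states and rejects 1. Item 6 passes 1 and rejects 5. The rules agree on 0 of 6, and the set {*f* ≥ 1} ∩ {*f* < 1} is empty.

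**Which direction was meant.** Of the 13 screening items, 12 state a reason to exclude; item 6 alone states the eligible condition. All five categories on the baseline sheet imply a positive answer to item 6, and the only kind of woman the form would pass has no category to tick. Both facts point to the direction in section 5.2.

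**Whether a later step catches it.** Of the two items in the check at randomization, 0 concern bowel frequency.

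**Possible extent.** Section 13.0 gives 63 per group, inflated for 10% attrition: 63 / (1 − 0.10) = 70 per group, and 2 × 70 = 140 planned participants. If item 6 is corrected only in the heads of staff, each of these women meets a printed exclusion. Up to 140 of 140 of their screening sheets would then carry either a positive answer against enrolment or a negative answer that the baseline sheet contradicts.

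**After rewording item 6 to match section 5.2.** All five baseline categories pass both rules, and the below-weekly state fails both.

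**The case against.** The contradiction in the text is not in dispute. The case on the other side concerns its weight.

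- **It is a slip on a form that staff would soon notice.** Section 5.2 is clear, and used literally the form would reject almost every candidate, so the error would probably show at the first screening. This is plausible. But relying on staff to override a written instruction not to enrol is not a control, and no later check repairs it.
- **The baseline sheet is separate evidence on exclusion 9.** This stands. A ticked category shows a frequency of at least weekly, so the statement that compliance cannot be shown applies to the screening sheet, not to the whole record. A gap remains: with no category below weekly, a blank is ambiguous.
- **The figure of 140 is a ceiling, not a count.** This also stands. It is the planned number randomized, not the number screened, and it assumes informal correction throughout. The extracted text does not show whether each item has its own answer box or whether there is one overall answer. Even one overall negative answer would be contradicted by the baseline sheet under the list as printed.
- **The two phrases may not be perfect complements.** A woman who averages about one movement a week but misses some weeks might, on a loose reading, pass both. This is marginal and does not rescue the item.
- **The table only restates a negation.** True; it sets out the consequence category by category and adds no independent evidence.

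**Conclusion.** The concern holds. As printed, screening item 6 is the logical reverse of exclusion 9: agreement on 0 of 6 frequency states, and none eligible under both. This takes both phrases in their ordinary sense, as statements about usual weekly frequency. The form is an operative eligibility rule that would enrol the wrong population if followed, so it must be corrected.

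The limits are equally clear. The documents do not show how the form was used, so the number of women affected is unknown; 140 is the ceiling among planned participants. Screening comes before 1:1 randomization and is identical for both arms, so the error does not bias the comparison between arms. The 63 per group, inflated to 70, is untouched.

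**What to change.** Reword item 6 so that a positive answer means exclude, in line with section 5.2, item 9; for example, *Baseline bowel movements less often than once a week*. Reissue the form.

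For any woman already screened, compare the screening answer and the recorded baseline frequency with section 5.2. Query any blank baseline frequency, because the sheet offers nothing below weekly.

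The cost is one line on a form and a minor amendment, plus a check of existing sheets if screening has begun. Design, sample size and analysis do not change.

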**If Yes to any of the above, do not enroll.**

# Prunes Data Collection Sheet

## Baseline data collected at time of study enrollment

Participant number # \_\_\_\_\_

Age \_\_\_\_\_ years

Race            White    Black or African American    Asian  
                  American Indian or Alaska Native    Native Hawaiian or Pacific Islander  
                  Other    Multiple races

Hispanic Ethnicity            Yes            No

Parity \_\_\_\_\_

Height            \_\_\_\_\_ cm

Weight            \_\_\_\_\_ kg

Menopausal            Yes            No            Unsure/Not known

Baseline frequency of bowel movements

Multiple times daily            Once a day            Once every other day  
 Twice a week            Once a week

Have you needed to use a laxative at any time in the last 3 months?            Yes            No

Do you take fiber daily or almost daily?            Yes            No

Are you on any of the following medications on a regular basis?            Yes            No

Antimuscarinics (such as Detrol, Ditropan)            Yes            No            No

Iron            Yes            No            No

Calcium channel blocker (such as nifedipine, amlodipine, verapamil, diltiazem)            Yes            No            No

Opioids (such as Percocet, Oxycodone, Tramadol, etc.)            Yes            No            No

Tricyclic antidepressant (such as amitriptyline, imipramine)            Yes            No            No

Bristol Stool Scale (Describe usual stool consistency) \_\_\_\_\_ (Indicate number)

### Bristol stool chart

Type 1		Separate hard lumps, like nuts (hard to pass)
Type 2		Sausage-shaped but lumpy
Type 3		Like a sausage but with cracks on its surface
Type 4		Like a sausage or snake, smooth and soft
Type 5		Soft blobs with clear-cut edges (passed easily)
Type 6		Fluffy pieces with ragged edges, a mushy stool
Type 7		Watery, no solid pieces, Entirely liquid

# Prunes Data Collection Sheet

## Data collected at time of randomization

Are any of the following exclusion criteria met?                      Yes                      No

1. Intraoperative enterotomy or any bowel surgery (not including posterior colporrhaphy) performed at the time of surgery
2. Patient unable to initiate oral intake on post op day 1 for any reason

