## 3.0 STUDY DESIGN

3.1 This is a prospective, randomized control trial.

3.2 Identification of Subjects:

All potential participants will be identified in the Gynecology or UroGynecology clinic at Los Angeles County-University of Southern California (LAC+USC) Medical Center. On average, between 8-10 patients undergo benign gynecologic surgery with overnight stay per week.

3.3 Recruitment of Participants:

Each eligible participant will be approached in person by one of the study investigators and invited to participate in the study. The informed consent will be reviewed in detail with a physician and the potential participant will be given time to ask questions. The potential participant will be allowed to take a copy of the consent home to review and discuss with family or friends.

3.4 Evaluation Pre-Intervention:

Clinical information will be collected.

3.5 Intervention:

1. Participants that undergo benign gynecologic surgery without intraoperative complications that are admitted overnight will be randomized to one of two groups.

2. Participants in the treatment arm will receive a 12 oz package of prunes on the morning of postoperative day 1.

3. All participants will receive the standard 100 g docusate sodium twice daily. Participants in the treatment arm will be instructed to consume 4 oz prunes (12 prunes) daily.

4. Additional laxatives will not be routinely given. There will be additional laxative medications (Milk of Magnesia) available for participants as needed, and it will be recorded that additional laxatives were needed.

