#### 10.0 CRITERIA FOR EVALUATION AND ENDPOINT DEFINITIONS

The outcome status of all eligible patients will be reported. All eligible patients who begin treatment will be included in the analysis.

Primary endpoints: Time to first bowel movement (in hours)

Secondary endpoints:

1. Stool consistency of the first bowel movement as classified by the Bristol Stool Scale (The stool types are categorical variables, and we will evaluate the differences in the frequencies of the responses by treatment status with a chi-square test)
2. Pain with bowel movement measured (Likert scale, and assessed using t-test or non-parametric methods as appropriate)
3. Satisfaction with bowel regimen (Likert scale, and assessed using t-test or non-parametric methods as appropriate)
4. Satisfaction with surgery overall (Likert scale, and assessed using t-test or non-parametric methods as appropriate)
5. Requirements for laxative (yes or no, assessed as categorical variables and evaluated by chi-square test)
6. Compliance with docusate (percentage of medications consumed, and assessed using t-test or non-parametric methods as appropriate)
7. Compliance with prunes (percentage of prunes consumed, and assessed using t-test or non-parametric methods as appropriate)

8. Adverse events of extreme bloating or flatulence (yes or no, assessed as categorical variables and evaluated by chi-square test)

Compliance with prune consumption will be defined as reported successful consumption of 2/3 of the assigned prunes.

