# Prunes Data Collection Sheet

## Self administered survey

Have you had a bowel movement since surgery? Yes No

If Yes, When did you have your first bowel movement?

Date \_\_\_\_\_ Time \_\_\_\_\_

How *painful* was your first bowel movement?

Not at all painful 0    1    2    3    4    5    6    7    8    9    10 Very painful

Which picture best describes your bowel movement (Circle one number)?

1    2    3    4    5    6    7

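### The day-1 randomisation check does not ask about a bowel movement since surgery, so a few women may be randomised with their primary outcome already fixed

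*Combined protocol and SAP*

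**What the plan says.** Section 6.3 sets the moment of allocation: "On morning of post-operative day 1, participants who do not meet exclusion criteria will be randomized". Section 3.5 puts the start of treatment at the same point: "Participants in the treatment arm will receive a 12 oz package of prunes on the morning of postoperative day 1".

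The Appendix III sheet completed at randomisation lists two reasons not to randomise: "Intraoperative enterotomy or any bowel surgery (not including posterior colporrhaphy) performed at the time of surgery" and "Patient unable to initiate oral intake on post op day 1 for any reason". The rest of that sheet covers bowel preparation, indication, procedures, blood loss and surgery times. In section 5.2 the one criterion on bowel movements is "Baseline frequency of bowel movements less than weekly", which describes the woman's habit before surgery. The screening questionnaire likewise asks only about usual weekly frequency.

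The primary endpoint in section 10.0 is the time to first bowel movement in hours, with no starting point given. Objective 2.1 places it after surgery, and the self-administered survey asks "Have you had a bowel movement since surgery", then for the date, time, pain and stool type of the first one. Section 10.0 analyses all eligible patients who begin treatment. The available pages contain no rule or sensitivity analysis for a bowel movement that precedes randomisation.

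**The concern.** The clock starts at surgery, but treatment starts the next morning. A woman who has a bowel movement in between passes every eligibility check, is randomised and is analysed. Her primary endpoint cannot respond to her allocation, and two secondary endpoints (pain and stool type at the first bowel movement) also describe a pre-treatment event.

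What is at stake is sensitivity. Such women contribute a true difference of zero to the primary comparison and pull the mean difference towards zero. The planned size has little slack: 63 per arm is the smallest whole number that reaches 80% power under the plan's assumptions.

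**Working it through.** **Inputs from the documents.** Section 13.0: difference 12 h, SD 23.7 h, two-sided 0.05, 80% power, 63 per arm, 70 after 10% attrition. Section 1.1: average time to bowel movement 4 days ± 1.5 days, that is 96 h and 36 h.

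**Assumptions.** Times follow a normal distribution. Randomisation falls 16 to 24 h after surgery (the documents give only the morning of day 1). The 12 h effect applies in full to women still at risk, and the SD stays at 23.7 h in the power calculation.

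**Step 1: the plan's own figure.** For a two-sample t-test with standardised difference 12/23.7 = 0.506, the exact solution is 62.2 per arm, rounded up to 63; 63/0.9 = 70. Both stated figures reproduce. Power at 63 per arm is 80.5%.

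**Step 2: share with an event before randomisation.** q = Φ((h − 96)/SD).

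| SD | h = 16 | h = 24 |
|---|---|---|
| 36 h (section 1.1) | z = −80/36 = −2.22, q = 1.3% | z = −72/36 = −2.00, q = 2.3% |
| 23.7 h (section 13.0) | z = −80/23.7 = −3.38, q below 0.1% | z = −72/23.7 = −3.04, q = 0.1% |

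Of 140 women, 1.3% is 140 × 0.013 = 1.8 and 2.3% is 140 × 0.023 = 3.2. At 0.1% the expected number is 0.14, so most likely none.

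**Step 3: effect on power.** If a share q in each arm cannot respond, the expected difference is 12 × (1 − q). The t-test power at 63 per arm is then:

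| q | Difference | Power |
|---|---|---|
| 0 | 12.00 h | 80.5% |
| 0.1% | 11.99 h | 80.4% |
| 1% | 11.88 h | 79.7% |
| 2.3% | 11.72 h | 78.7% |
| 5% (assumed) | 11.40 h | 76.4% |

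At q = 2.3%, restoring 80% would take 65.1 per arm, rounded up to 66, against the planned 63. The 5% row is illustrative and rests on no figure in the documents.

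**Step 4: direction.** Events before allocation cannot depend on the arm, so q has the same expectation in both groups. The estimate shrinks towards zero. If prunes have no effect, the difference stays centred on zero.

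The model gives every woman still at risk the full 12 h. A woman due within 12 h of randomisation could not gain that much, but the extra item would not remove her, so that shortfall is not part of this point.

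**The case against.** Four objections carry weight.

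- **Size.** On the documents' figures this is at most about 3 women in 140 and under 2 points of power. That stands. Shares of 6% to 9% can be produced by assuming a mean of 72 h with SD 36 h, but that mean is not in the documents. In the other direction, the 4-day average is for women given no bowel intervention, whereas all women here receive docusate. The true share may therefore be higher, and the documents give no docusate-alone figure to settle it.
- **The dilution model is a choice.** Section 13.0 states 12 h as the mean difference between groups. If it already averages over everyone randomised, no power is lost against the plan. That also stands, and it is why the power figures are conditional.
- **Early events can largely be found afterwards.** The forms record surgery end time and the date and time of the first bowel movement, so most could be flagged for a sensitivity analysis. This stands in part. The randomisation sheet has no field for the time of randomisation, and only the prune arm has a diary of its first prune, so events on the day-1 morning could not be ordered in the same way in both arms.
- **Keeping these women is defensible as a pragmatic choice.** That is fair, but the plan does not state it as a choice.

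Three stronger readings should be resisted. A reader might infer that the comparison is biased; allocation cannot influence an event that came before it. A reader might infer that these women are uninformative; they still contribute to compliance, laxative use, satisfaction, and bloating or flatulence, which are mostly or wholly observed after randomisation. A reader might infer that restricting the analysis to those who begin treatment would drop early events from the prune arm only. The documents do not say that a woman would skip prunes for this reason, and section 7.3 does not list a bowel movement as a ground for removal.

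**Conclusion.** The gap is real and small. No eligibility list and no item on the day-1 sheet removes a woman whose first bowel movement has already happened, so her primary endpoint, pain score and stool type can be fixed before allocation.

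The consequence is slight dilution, with validity intact. With the protocol's 96 h mean, the affected share runs from about 0.1% or less to 2.3%, and power is about 78.7% or better. These figures rest on normality, on 16 to 24 h between surgery and randomisation, and on the 12 h effect applying to women still at risk. The share under docusate is unknown; if it were 5%, power would be 76.4%. The documents do not support calling this a material loss of power. It is worth correcting because the correction is so cheap.

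**What to change.** Add a third item to the Appendix III check at randomisation: *Bowel movement since surgery? If yes, do not randomize.* Add the same criterion to section 5.2 so that the two lists agree. In section 10.0, state that time runs from the end of surgery to the first bowel movement. Once these women are excluded, the first bowel movement since surgery is also the first after randomisation, so no further change to the endpoint wording is needed.

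Because the item acts before allocation, it leaves the randomised comparison intact. The planned 63 evaluable and 70 randomised per group can stay.

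The cost is one tick box and one sentence. A few consented women will not be randomised (up to about 3 in 140 on the protocol's figures, possibly more under docusate), so recruitment takes slightly longer and the results apply to women who have not yet had a bowel movement by the morning of day 1.
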